Maintaining Continuous Positive Airway Pressure (CPAP) is a common form of support to patients with respiratory distress admitted to Intensive Care Units (ICU) of industrialized countries. Nasal CPAP (NCPAP) is effective in reducing hypoxemia and contributes to reducing the number of children requiring endo-tracheal intubation and mechanical ventilation. CPAP is most frequently delivered to neonates using conventional mechanical ventilators, which involves much higher costs. There are other ways of delivering CPAP. Bubble-CPAP is a simple, non-invasive delivery system with potential to reduce hypoxemia in neonates with acute respiratory failure. Equipment of bubble CPAP is now available at a fraction of the cost of mechanical ventilators. Bubble-CPAP has several advantages over mechanical ventilation such as lower cost, easier application by nursing staff and lower risk of complications. It therefore has potential as an inexpensive and affordable method of delivering CPAP in developing countries. Moreover, all the necessary equipment could be made locally.

Humidified high flow air / O₂ supplementation has been suggested in case series to be useful in reducing the need for mechanical ventilation in infants with bronchiolitis. However, there have been no randomized trials to compare it with bubble CPAP or with standard O₂ supplementation by nasal prongs. It is simple to apply, but requires careful monitoring and delivers uncertain levels of CPAP.

Hypoxaemia is documented in nearly half of the patients admitted to the ICU of the Dhaka Hospital of ICDDR,B and many of them present with impending respiratory failure. Children under five with severe pneumonia nearly always have associated severe malnutrition, and many receive mechanical ventilation. This is expensive and is associated with high complication and mortality rates – the death rate was 81% among the **26 children under five who were ventilated due to respiratory failure between January and October, 2010**. There are no published data on the use of bubble-CPAP in children, beyond the newborn period, or in the treatment of pneumonia in developing countries, and no controlled trials of CPAP. We propose to conduct a study to compare the efficacy of (a) bubble CPAP with that of (b) the standard O₂ supplementation by nasal prongs and (c) humidified high flow nasal cannula air / O₂ in the management of hypoxic children with respiratory failure admitted to the ICU of the Dhaka Hospital of ICDDR,B.

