
KEY PERSONNEL (List names of all investigators including PI and their respective specialties)

Name	Professional Discipline/ Specialty	Role in the Project
1. [name]	Paediatric respiratory physician	Principal Investigator
2. [name]	Internist	Co-PI
3. [name]	Medicine specialist/Pulmonologist	Co-PI
4. [name]	Paediatrician Anaesthetist/Intensive care specialist	Co-PI
5. [name]	Paediatrician/Intensive care specialist	Co-PI
6. [name]	Paediatrician	Co-PI
7. [name]	Nutritionist and Epidemiologist	Co-I
8. [name]	Internist/Paediatrician	Co-I
9. [name]	Internist	Co-I

Description of the Research Project

Hypothesis to be Tested:

Please briefly list the Hypothesis to be tested and provide the scientific basis of the hypothesis, critically examining the observations leading to the formulation of the hypothesis.

On the basis of the above background, our primary hypothesis is that:

1. In children with severe pneumonia and hypoxaemia the probability of treatment failure (see definition below) will be significantly lower when respiratory support is initially provided by bubble-CPAP compared to standard nasal prong O₂ and humidified high flow for children with severe pneumonia and hypoxaemia.

Our secondary outcomes are:

2. Mortality rate at hospital discharge, rate of need for mechanical ventilation, rates of nosocomial infections (if clinical features of new episode of infection develops 48-72 hours after admission to a hospital), rates of multi-organ failure at 7 days, length of hospital stay, rate of absconding, bacterial aetiology and rates of isolation of TB will be significantly different when treatment is provided by bubble-CPAP, compared to standard nasal prong O₂ and humidified high flow for children with severe pneumonia and hypoxaemia

Specific Aims:

Describe the specific aims of the proposed study. State the specific parameters, biological functions, rates, processes etc. that will be assessed by specific methods.

The specific objectives of the study are:

Primary objective:

To evaluate the rates of treatment failure (see definition below) in neonates and children with severe pneumonia and hypoxaemia treated by bubble-CPAP, humidified high flow (2 litres per kg per min) air / O₂ mix by nasal cannula, and standard treatment using only oxygen (0.5 – 2 litres per min) via nasal cannula.

Secondary objectives:

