1.3 Intervention and comparators

Children under five admitted to the SCU of ICDDR, B with pneumonia and hypoxaemia will be studied. This study will evaluate the proportions of deaths in children under five in three treatment arms.

We will use sealed envelopes to randomly assign the children to one of three treatment arms. In first arm, children will receive bubble CPAP (bubble CPAP pressure of 5 to 10 cm of H₂O); in 2nd arm, children will receive standard O₂ supplementation by nasal cannula at 0.5 – 2 L/min (or 4l/min for children > 2 years); in the 3rd arm, children will receive humidified high flow air / O₂ mix at 2 L/kg/min (maximum 12L/min) through nasal cannula from a high flow generator. The three arms will be compared for rates of treatment failure (see below).

During the study period, children (whether under ventilation or not) in all three study arms will also receive standardized hospital management for pneumonia and malnutrition.

"Treatment failure" will be standardized, based on clinical and monitoring data.

During the study period any child from either study group who develops the features of "clinical failure" (any two of three criteria in the definition below) will be managed according to best practice in the clinical context. If children fail the arm of standard 2L nasal cannula O₂ they should be rescued with B-CPAP or humidified high flow air / O₂ mix at 2 l/kg/min through nasal cannula after further randomization. However, if children fail the arms of humidified high flow air / O₂ mix at 2 l/kg/min or bubble CPAP, they will receive mechanical ventilation. "Clinical failure" is the criteria to be followed to decide intubation and mechanical ventilation.

Laboratory investigations:

Routine: Blood (5.0 ml) for total and differential count of white blood cell (WBC), haematocrit, culture and sensitivity, serum electrolytes and creatinine, stool culture and urine culture, chest radiograph (CXR) on admission. Venipuncture for blood culture collection was performed by the attending physician under aseptic precautions. The puncture site was disinfected using two agents (10% povidone iodine followed by 70% rectified spirit) and left to dry for 30 to 60 seconds. 2.0 mL of blood was collected and injected into standard pediatric blood culture bottles and sent to our icddr,b microbiology laboratory where it used to be processed for the culture and sensitivity following standard procedure.

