We are intending to perform an interim analysis of the data to see any significant difference among the treatment arms. If one of the three treatment arms will show any significant beneficial effect, we will inform the ERC and simultaneously stop the study without any further delay due to ethical obligation and implement the best treatment modality of oxygen delivery for the hospital patients.

After the completion of the analysis, important results will be incorporated to the national pneumonia guideline. It is prudent to mention that the children who will be “absconded” from our study after randomization due to any reason will also be included in our primary analysis and will be considered them as INTENTION TO TREAT (ITT) ANALYSIS. Thus, ITT analysis should be, any child who, after randomization:

- Fulfils the criteria for treatment failure as defined in the proposal
OR
- Receives intubation and / or mechanical ventilation
OR
- Dies
OR
- Left against medical advice while still on the allocated respiratory support

Outcome variables

1. The primary outcome will be treatment failure (see definition above).
2. The secondary outcomes will be:
 - a. Mortality rate calculated at hospital discharge
 - b. Rate of need for mechanical ventilation
 - c. Rates of nosocomial infections
 - d. Rates of multi-organ failure at 7 days
 - e. Length of hospital stay

- f. Rate of absconding
- g. Bacterial aetiology
- h. Rates of isolation of TB

Ethical Assurance for Protection of Human Rights

Describe the justifications for conducting this research in human participants. If the study needs observations on sick individuals, provide sufficient reasons for using them. Indicate how participants rights will be protected, and if there would be benefit or risk to each participants of the study.

The study will be performed in compliance with the ‘Declaration of Helsinki’ (2000), the International Conference of Harmonization (ICH), Tripartite Guidelines, Guideline for Good Clinical Practice (GCP). These procedures ensure the protection of the rights and the integrity of the study participants, adequate and correct conduct of all study procedures, adequate data collection, adequate documentation and adequate data verification.

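### Nasal-prong failures get an extra non-invasive rescue step that bubble CPAP and high-flow failures do not, so the ventilation rate against nasal prongs does not measure the allocated device like for like

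*Protocol*

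**What the plan says.** Section 1.3 of the protocol sets different consequences for the same event, clinical failure.

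- Standard nasal-prong arm: "they should be rescued with B-CPAP or humidified high flow air" mixture, the latter delivered "through nasal cannula after further randomization". This is a second non-invasive step.
- The other two arms: children who fail high flow "or bubble CPAP, they will receive mechanical ventilation".

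The same section also says, for any study group, that clinical failure is handled by best practice. It closes by saying that clinical failure "is the criteria to be followed to decide intubation and mechanical ventilation", with no restriction by arm. It does not say what follows when the re-randomised rescue itself fails.

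The list of outcome variables includes "Rate of need for mechanical ventilation" as secondary outcome b. The hypothesis section says that this and the other secondary outcomes "will be significantly different when treatment is provided by bubble-CPAP, compared to standard nasal prong" oxygen and high flow. The secondary objectives repeat it, and the data analysis section sets a 0.05 threshold for outcomes other than the primary. Neither the hypothesis nor the outcome list mentions the extra rescue step.

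The primary outcome (section 1.5) is a composite: clinical failure (component A), intubation or ventilation (B), death in hospital or within 30 days of discharge (C), or leaving against advice while still on the allocated support (D).

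**The concern.** Under the rules as written, one failure takes a CPAP or high-flow child to the ventilator. A nasal-prong child who fails once is first offered another device, and some of these children will recover on it. A lower ventilation rate in the prong arm can therefore reflect the added rescue step and not the first-line device.

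The protocol's rationale includes the hope that bubble CPAP will spare children ventilation. If the secondary outcome is read as a device effect, a trial in which CPAP performs exactly as assumed could report no reduction in ventilation, or an increase. Ventilation is also component B of the primary outcome, and the monitoring board may look at all components, so the same artefact could surface in safety review.

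**Working it through.** **Inputs.** From section 2 (sample size): treatment failure 30% with standard care and 18% with the new intervention, type 1 error 0.03, 90% power, factor 11.9, 295 per group before drop-out. From section 1.3: the rescue rules above. Not in the protocol: q, the proportion of re-randomised prong failures who also fail rescue support. It is assumed, and its range is shown.

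**Reproducing the plan's figure.** (0.30 × 0.70 + 0.18 × 0.82) / 0.12² × 11.9 = 0.3576 / 0.0144 × 11.9 = 295.5, which agrees with the stated 295. The 30% and 18% are therefore the rates on which the trial is built.

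**Ventilation rates implied by the rescue rules.** Three assumptions are needed: the composite rates stand in for clinical failure, every CPAP failure is ventilated, and every failed rescue is ventilated.

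- CPAP arm: 18%.
- Prong arm: 30% × q.

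| q (assumed) | Prong arm | CPAP arm | CPAP minus prong, points |
|---|---|---|---|
| 18% | 5.4% | 18% | +12.6 |
| 30% | 9% | 18% | +9 |
| 50% | 15% | 18% | +3 |
| 60% | 18% | 18% | 0 |
| 80% | 24% | 18% | −6 |
| 100% | 30% | 18% | −12 |

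Break-even: q = 0.18 / 0.30 = 0.60.

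**Size of the shift.** If every clinical failure were ventilated in every arm, the difference would be 18% − 30% = −12 points, in favour of CPAP. The extra step moves it by 30% × (1 − q) against CPAP, which is positive for every q below 100%. For example, at q = 30% the shift is 21 points, from −12 to +9.

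**If CPAP had no benefit.** With 30% failing in both arms, ventilation would be 30% on CPAP against 30% × q on prongs, so CPAP would look worse for every q below 100%.

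**Chance of a significant result in the wrong direction.** At q = 30% and 295 per arm, the expected counts are about 27 (0.09 × 295) and 53 (0.18 × 295). A two-sided test at 0.05 then has about 89% power to find more ventilation on CPAP.

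**Which contrasts are touched.** High flow versus prongs has the same structure: with a high-flow failure rate h, the break-even is q = h / 30%. Bubble CPAP versus high flow has one rescue rule in both arms, so the shift is absent. In the primary composite, a prong child who reaches clinical failure is already counted under component A before rescue begins. The later step cannot remove that event.

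**The case against.** The strongest reply is that a randomised intention-to-treat comparison of arms, each with a fixed rescue path, is valid: it compares strategies. That stands, and it is why the point concerns what the outcome is said to measure and not the validity of the randomised contrast. It may also be said that the reading of a secondary outcome belongs in a statistical analysis plan, which is not shown here. But the hypothesis and the rescue rules are both fixed in the protocol, and together they do not fit.

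The objections to the arithmetic also stand in part. The 30% and 18% are composite rates that include deaths after discharge and departures against advice, which need not lead to ventilation. The 60% break-even holds only if clinical failure is the same share of the composite in both arms. Ventilation after a failed rescue is assumed. Children who have already failed once are a selected group, so q may be well above 18%.

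Three stronger readings are tempting and are not supported:

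- A reader might infer that the main comparison is compromised. Component A largely protects it.
- A reader might infer that CPAP will appear worse on ventilation. That depends on q, which the protocol does not give; above 60% CPAP still looks better, though by less.
- A reader might infer that mortality is biased against CPAP, because the project abstract reports that "the death rate was 81% among the" 26 young children ventilated for respiratory failure. That is a crude rate in very sick children and does not show that earlier ventilation raises deaths. The background section itself names late start of ventilation among the complications tied to high mortality, which could act the other way. No direction for mortality follows.

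The statements in section 1.3 can be read in sequence, from general principle to arm-specific rescue to ventilation criterion. The last is still worded without regard to arm, so it needs reconciling, but it is a matter of wording.

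**Conclusion.** The point holds in a limited form. Against nasal prongs, the rate of need for ventilation is not a like-for-like measure of bubble CPAP or of high flow. As long as some rescued prong children avoid ventilation, the contrast is shifted against both devices.

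Under the stated stand-in rates and assumptions, the sign of the CPAP–prong contrast reverses for q below 60%, and the benefit is understated for q between 60% and 100%. The direction of the shift comes from the rescue rules; its size rests on q and on the use of composite rates for clinical failure. One secondary outcome is affected in two of its three pairwise contrasts.

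**What to change.** - Make bubble CPAP versus high flow the device comparison for mechanical ventilation.
- Against nasal prongs, use clinical failure, or escalation beyond the allocated support, as the device comparison. The downside is overlap with the primary outcome. In an open trial the decision to escalate to another nasal device may also differ from the decision to ventilate, so the criteria-based clinical failure is the cleaner of the two.
- Still report ventilation against nasal prongs, labelled as a comparison of strategies (first-line support plus rescue) and not as a device effect.
- Label mortality and nosocomial infection against prongs as strategy comparisons too, without claiming a direction of bias.
- Reconcile the statements in section 1.3 on what follows clinical failure (best practice, arm-specific rescue, criterion for intubation), including what follows a failed rescue. No clinical rule is proposed here.

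The cost is the wording of one secondary outcome and its analysis, plus a clarification in section 1.3. Clinical failure and ventilation are already recorded for the primary outcome, so no new data are needed and the sample size does not change.

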1.4 Measurements

All children will be monitored for by pulse oximetry for arterial O₂ saturation, respiratory rate, lower chest wall in-drawing, intercostal retraction, head nodding, cyanosis, tracheal tug, heart failure (defined by the presence of tachypnea, tachycardia, gallop rhythm, hepatomegaly, pedal oedema, basal crackles). Pulse oximetry monitoring is the most accurate non-invasive and real time measurement of respiratory status, which along with clinical signs will be the main method of monitoring. Arterial or capillary blood gas analyses will be done for children failing to maintain saturation ($\geq 90\%$ with allocated treatment), or if there is concern about hypercarbia or acidosis.

Describe the availability of physical facilities at site of conduction of the study. For clinical and laboratory-based studies, indicate the provision of hospital and other types of adequate patient care and laboratory support services. Identify the laboratory facilities and major equipment that will be required for the study. For field studies, describe the field area including its size, population, and means of communications.

This study will be conducted at the Dhaka Hospital of ICDDR,B, Dhaka, Bangladesh. This hospital is located in Dhaka city, the capital of Bangladesh. It provides care and treatment to around 110,000 diarrheal patients with or without associated complications and with or without other health problems each year. The vast majority of the patients come from poor socio-economic backgrounds from urban and peri-urban Dhaka, the capital city of Bangladesh.

Patients attending this hospital are first assessed by an experienced triage nurse, which include assessment of the type of diarrhoea and degree of dehydration, and presence of other health problems including ALRI/ pneumonia, severe malnutrition, impaired mental status (convulsion), and sepsis. They redirect non-diarrhoeal patients to other appropriate city hospitals in the city. Based on assessment of diarrhoeal patients, those with uncomplicated illness without signs of dehydration are referred to the Out Patient Unit for 1-2 hours of observation, maintenance of hydration using ORS solution, and for provision of health education to the mothers/caregivers. Those with some and severe dehydration but without any associated health problems are admitted to Short Stay Ward (SSW) for correction of dehydration and maintenance of hydration using ORS and/or intravenous fluids, provision of antimicrobial therapy as appropriate, with an average stay of 24 hours. Those with associated complications of diarrhoea and/or associated health problems are referred to a physician for assessing the need for admission to either the Longer Stay Ward (LSW) or Acute Respiratory Ward (ARI) or to the Special Care Word (SCU) depending on the clinical severity. The usual associated conditions include difficult respiration, cyanosis, apnoea, hypothermia or hyperthermia, marked lethargy or comatose condition, poor peripheral perfusion not attributable to severe dehydration. Those hospitalised in SSW for 120 hours are assessed by hospital clinicians for possible admission to LSW and further workup and management. After admission to the LSW/ARI/SCU the attending physician obtained medical history, performs thorough clinical examination, makes a problem list including differential diagnoses for each of them, arranges for required laboratory workups, and develops the treatment plan following standard guidelines of the hospital. They also perform bedside procedures such as sampling blood, performing lumbar puncture etc. Oxygen saturation is determined by pulse oximeter when necessary, and blood glucose estimated by bedside Glucocheck machine in nearly all patients admitted to the LSW/ARI /SCU.

Respiratory ward Infrastructure:

An independent acute respiratory infection treatment unit was established right at the entrance to the hospital, and started functioning on 6 September, 2009. Patients reporting to Dhaka Hospital were rapidly screened for respiratory symptoms such as fever, cough, myalgia, headache, chills, fatigue, running nose, sore throat, rapid breathing and difficulty in breathing. Patients with these symptoms were referred to the respiratory triage where they were assessed following the hospital guidelines and relevant information was entered into the hospital's electronic database. Patients with any form of pneumonia (non-severe, severe, and very severe), bronchiolitis, asthma, bronchitis, pleural effusion, empyema, lung abscess, tuberculosis, and any other common respiratory problems are admitted in the ward. Others were referred to the usual diarrhoea triage of the hospital. Sufficient staff provide 24 hour cover from all cadres (doctors, nurses, health workers and auxiliary staff). This facility was provided with all necessary supplies including a portable X-ray machine, Ambu bags, large oxygen cylinders, pulse oxymeters, disposable gloves, disinfectants and medication (e.g. antibiotics and other medicines). Pulse oximetry is routinely performed to

evaluate arterial oxygen saturation, and additional tests were performed if there were clinical indications. Vital signs were monitored, and stool and urine output was measured and recorded 8 hourly. Therapy is decided on the basis of clinical evaluation, results of the laboratory tests, and the hospital guidelines for management of respective respiratory illness.

Data Safety Monitoring Plan (DSMP)

All clinical investigations (biomedical and behavioural intervention research protocols) should include the Data and Safety Monitoring Plan (DSMP) to provide the overall framework for the research protocol's data and safety monitoring. It is not necessary that the DSMP covers all possible aspects of each element. When designing an appropriate DSMP, the following should be kept in mind.

- a) All investigations require monitoring;
- b) The benefits of the investigation should outweigh the risks;
- c) The monitoring plan should commensurate with risk; and
- d) Monitoring should be with the size and complexity of the investigation.

Safety monitoring is defined as any process during clinical trails that involves the review of accumulated outcome data for groups of patients to determine if any treatment procedure practiced should be altered or not.

Data safety Monitoring will be rigorously performed throughout the course of the study mainly by an independent DSMB who will visit randomly to review the forms for completeness, legibility, and internal consistency. This trial has a formally constituted DSMB. This DSMB consists of senior scientists from IcdDr,b, many who are independent of the trial, some of whom also sit on the icddr,b's Ethics Research Committee. Other members of the DSMB for this study include [name] from the University of Melbourne. The DSMB will meet every 6 months and if they feel the necessity they may evaluate data on all components of the composite primary outcome, and all adverse events. If there are any differences in the primary outcome or the adverse events that are not included in the primary outcome between the three groups, the trial will be stopped. IcdDr,b's ERC required reporting of all serious adverse events (SAE) within 24 hours; for this study all adverse events (AE) will also be reported by the study investigators to the DSMB within 24 hours of their occurrences using a standard case reporting form. As this is an open trial the implications of an adverse event can be better interpreted throughout the conduct of the trial than would be possible if any blinding was involved. The DSMB will have full access to all case reporting forms and trial data, not only every 6 months, but whenever it is appropriate if there are any concerns over excess adverse events or unbalanced events between the three study groups. All aspects of intervention and interpretation will be performed according to rigorously standardized standards of procedures (SOPs).

Data Analysis

Describe plans for data analysis. Indicate whether data will be analysed by the investigators themselves or by other professionals. Specify what statistical software packages will be used and if the study is blinded, when the code will be opened. For clinical trials, indicate if interim data analysis will be required to determine further course of the study.

Questionnaires will be visually scanned soon after interview and marked for omissions, inconsistencies or mistakes that will be addressed immediately. Data will be entered into a personal computer using Statistical Package for Social Sciences, version 12.0 Windows, (SPSS, Chicago, IL) after creating a template for each data entry file with appropriate logical and consistency

checks. Data will be continuously entered as it is being generated in hospital, laboratory, and field. All data will be entered a second time, then consistency between two will be verified by matching with detected errors then necessary corrections will be made. In addition, data will be validated by a series of logical and range checks, producing summary statistics and tables. Data will be immediately copied on the hard disks of two computers as soon as data verification is complete.

Data analysis will be performed using the SPSS, version 12.0 Windows, (SPSS, Chicago, IL) and Epi Info (version 6.0, USD, Stone Mountain, GA). Data will be summarized and findings of one site will be compared with that of other sites(s). Statistical analyses will include descriptive as well as analytical methods. When the variable of interest is a categorical variable, the significance of differences will be evaluated by chi-square test or Fisher exact test. When the main outcome measures are continuous variables, the statistical significance of two groups (bubble CPAP vs. standard low flow or humidified high flow) will be determined by students “t” test or Mann-Whitney test as appropriate. A probability of less than 0.05 will be considered statistically significant except primary outcome (probability of less than 0.03 will be considered statistically significant for primary outcome). Strength of association will be determined by calculating odds ratio (OR) and 95% confidence intervals (CI). Finally, regression analyses will be performed for more definitive conclusions where treatment failure will be the dependent variable and factors associated with treatment failure by univariate analysis will be independent variables. Regression analyses will also be performed to evaluate independent predictors for death where deaths will be the dependent variable and factors associated with deaths in our study population by univariate analysis will be independent variables.

We are intending to perform an interim analysis of the data to see any significant difference among the treatment arms. If one of the three treatment arms will show any significant beneficial effect, we will inform the ERC and simultaneously stop the study without any further delay due to ethical obligation and implement the best treatment modality of oxygen delivery for the hospital patients.

After the completion of the analysis, important results will be incorporated to the national pneumonia guideline. It is prudent to mention that the children who will be “absconded” from our study after randomization due to any reason will also be included in our primary analysis and will be considered them as INTENTION TO TREAT (ITT) ANALYSIS. Thus, ITT analysis should be, any child who, after randomization:

- Fulfils the criteria for treatment failure as defined in the proposal
OR
- Receives intubation and / or mechanical ventilation
OR
- Dies
OR
- Left against medical advice while still on the allocated respiratory support

Outcome variables

1. The primary outcome will be treatment failure (see definition above).
2. The secondary outcomes will be:
 - a. Mortality rate calculated at hospital discharge
 - b. Rate of need for mechanical ventilation
 - c. Rates of nosocomial infections
 - d. Rates of multi-organ failure at 7 days
 - e. Length of hospital stay

- f. Rate of absconding
- g. Bacterial aetiology
- h. Rates of isolation of TB

Ethical Assurance for Protection of Human Rights

Describe the justifications for conducting this research in human participants. If the study needs observations on sick individuals, provide sufficient reasons for using them. Indicate how participants rights will be protected, and if there would be benefit or risk to each participants of the study.

The study will be performed in compliance with the ‘Declaration of Helsinki’ (2000), the International Conference of Harmonization (ICH), Tripartite Guidelines, Guideline for Good Clinical Practice (GCP). These procedures ensure the protection of the rights and the integrity of the study participants, adequate and correct conduct of all study procedures, adequate data collection, adequate documentation and adequate data verification.

The study will only be initiated after it has been approved by the Research Review Committee (RRC) and the Ethical Review Committee (ERC) of ICDDR,B. Before enrolment signed informed consent will be obtained from the adults and from the parents/guardians of the children. The consent form will be written in Bangla in a language and format that will be easily understood by the study subject of even little or no educational background. The consent form will be read out to the care-giver/legal guardian/parent of the study subject if he/she is unable to read. Signed consent or the left thumb impression will be obtained from the care-giver/legal guardian/parent for participation of the children in the study. Consent will be taken both for participation in the study and collecting samples as outlined in the different aims (Consent forms in appendices 5a, b and c).

Use of Animals

Describe if and the type and species of animals to be used in the study. Justify with reasons the use of particular animal species in the experiment and the compliance of the animal ethical guidelines for conducting the proposed procedures.

This study does not involve use of animals

Literature Cited

Identify all cited references to published literature in the text by number in parentheses. List all cited references sequentially as they appear in the text. For unpublished references, provide complete information in the text and do not include them in the list of Literature Cited. There is no page limit for this section, however, exercise judgment in assessing the “standard” length.

Please see the reference list

Dissemination and Use of Findings

Describe explicitly the plans for disseminating the accomplished results. Describe if and how the research findings would be shared with stakeholder, identifying them if known, and the mechanism to be used. Also describe what type

of publication is anticipated: working papers, internal (institutional) publication, international publications, international conferences and agencies, workshops etc. Indicate, if the project is linked to the Government of the People's Republic of Bangladesh through a training programme or a collaborative arrangement.

We hope that this study will explore to a better understanding of the compared usefulness of the bubble CPAP, and humidified high flow air / oxygen mix by nasal canula among children with severe pneumonia and hypoxaemia. This study should enable better models of high dependency intensive care to be developed in resource limited countries, and avoid excessive money being spent on Western style intensive care units. We will share the information with policy makers to create awareness about the compared usefulness of the bubble CPAP, standard oxygen therapy and humidified high flow by nasal canula for these children in Bangladesh.

The results of the study will be disseminated in several ways: (i) **this will use to defend the thesis of PhD for principal investigator ([name]) at the University of Melbourne.** (ii) The findings of the study will be disseminated through workshops and conferences at national and international level. Moreover, results will be published in reputed national, regional, and international journals.

Collaborative Arrangements

Briefly describe if this study involves any scientific, administrative, fiscal, or programmatic arrangements with other national or international organizations or individuals. Indicate the nature and extent of collaboration and include a letter of agreement between the applicant or his/her organization and the collaborating organization.

This study is a collaborative effort of researchers from the International Centre for Diarrhoeal Disease Research, Bangladesh (ICDDR,B) and the Centre for International Child Health (CICH), the Royal Children's Hospital, the Department of Paediatrics, the University Melbourne. Data analysis, interpretation, and publication will be done in close collaboration of the partners.

Institutional contracts will define the roles and responsibilities of each institution according to the following lines:

ICDDR, B:

Will provide research infrastructure, personnel, and conduct study in Bangladesh, plus co-supervision.

Centre for International Child Health, The Royal Children's Hospital, Department of Paediatrics, The University Melbourne:

Provides technical assistance, and co-supervision of PhD of the PI, and assistance with funding.

Biography of the Investigators

Give biographical data in the following table for key personnel including the Principal Investigator. Use a photocopy of this page for each investigator.

